2. STUDY PROCEDURES

a. Procedures

Screening: Patients who have been recommended to undergo endoscopic sinus surgery by our department will be recruited for the study and informed of its purpose pre-operatively. SNOT22 scores (a quality of life survey well established in Rhinology) and Lund-Kennedy endoscopic exam scores (an quantitative clinical assessment of disease severity) will be recorded in their medical records. This is the same protocol performed for all patients seen in our clinic regardless of their enrollment in the study. Randomization and Treatment Groups: The patients that wish to participate will be randomized into two treatment arms by our nurse practitioner based on a random number generator. They will receive one of the following post-operative regimens: 1) oral steroid (treatment) + steroid spray (treatment) 2) oral placebo (control) + steroid spray (treatment) These medications will be manufactured and packaged by an independent compounding pharmacy, and prescribed by our nurse practitioner at the preoperative visit. Patients will begin their therapy on the first post-operative day. All oral steroid regimens will be given in our institution's standard 12 days taper, while topical steroids will be delivered via a metered dose nasal spray bottle for two weeks. All study patients will receive identical perioperative antibiotic therapy. We do not anticipate these medications to be an inconvenience to study patients as all proposed interventions are not different from routine post-operative care. In addition, patients undergoing surgery will have already trialed these medications as part of their pre-operative medical therapy. Surgery: Routine endoscopic sinus surgery will be performed per our institution's standard protocol. In this step there will be no difference in treatment from those patients not enrolled in the study. Post-Operative Care: At this point, patients will begin therapies according to the treatment arm to which they have been randomized. Study patients will attend post-operative appointments at identical time points to non-study patients. These will take place at the following intervals: Post-operative visit 1: 1-2 weeks Post-operative visit 2: 6-8 weeks Post-operative visit 3: 12-16 weeks Post-operative visit 4: 6 months Experimental therapy will finish after 2 weeks. At this visit, all patients will then be maintained on intranasal steroid spray and nasal saline irrigations, which is the commonly employed therapeutic standard. Thereafter, patients will, per standard protocol, be followed on an observational basis depending on the severity of symptoms and response to treatment. At each visit, as is done for all individuals, SNOT-22 and LundKennedy endoscopic exam scores will be repeated and recorded.

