
b. Procedure Risks

This study does not seek to evaluate a novel research procedure. Rather, we endeavor to determine if a procedure already in place nearly universally is, in fact, beneficial, as there is a

distinct lack of evidence of suggest so. Overall, we are investigating a procedural method that will have fewer side effects than the currently accepted practice.

c. Use of Deception in the Study

NA

d. Use of Audio and Video Recordings

NA

e. Alternative Procedures or Courses of Treatment

All reasonable alternatives are included as a treatment arm in this study. There is no standard of care that is being withheld from patients in any group.

f. Will it be possible to continue the more (most) appropriate therapy for the participant(s) after the conclusion of the study?

Yes, patients will stop all experimental therapies at the 2 week mark. They will then be placed on the typical post-operative regimen, which includes a nasal steroid spray and twice daily saline irrigations. They will continue to be followed in our clinic after the 4 week mark, and their therapies tailored to their current symptoms and the endoscopic appearance of the nasal cavity.

g. Study Endpoint(s)

Currently, our post-operative protocol dictates that patients will be seen in clinic at 1 week, 3 weeks, and 6 weeks after surgery. We will only slightly alter this timeline for study patients. At the 2 week appointment, all experimental therapies will be completed. Patients will then be started on intranasal steroid sprays and saline irrigations so as not to deviate for an extended period from currently accepted practices. We will use the final scheduled appointment at 4 weeks after surgery as the official end point for comparison of treatment arms. Additionally, outcomes evaluated will be the symptom questionnaire and the endoscopic exam score at each visit. If, during the course of follow up, one regimen proves to be clearly superior to another, the study will be terminated and patients will receive the optimal therapy. By power analysis, we require 50 patients to achieve statistical significance. If there is a clearly optimal therapy determined in these first 50 patients, we will end our research at that time. All patients will continue to be followed beyond 4 weeks depending on symptom severity and response to treatment

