Perioperative Oral Steroids for Chronic Rhinosinusitis Without Polyps

Statistical Analysis Plan

NCT02748070

July 2, 2020

[name], Principal Investigator
Stanford University
Stanford, California 94305

The planned sample size was 75 patients. By power analysis, we required 50 patients to achieve statistical significance. We collected outcome measures of SNOT-22 and Lund-Kennedy endoscopy scores at the following time points: preoperative baseline, and postoperatively at 1 week, 1 month, 3 months, and 6 months.

All statistical analyses were performed using Stata 15 (Stata Statistical Software: Release 15; StataCorp LP, College Station, Texas). SNOT-22 total scores, SNOT-22 subdomain scores, Lund-Kennedy endoscopic scores, and adverse effects were compared between prednisone and placebo groups at each time point using t-tests.

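### Separate t-tests at each visit leave later comparisons exposed to selectively missing scores, and no analysis tests whether the arm difference changes over time

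*SAP*

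**What the plan says.** The SAP lists the measurement times as "preoperative baseline, and postoperatively at 1 week, 1 month, 3 months, and 6 months". Its only comparative method is that "SNOT-22 total scores, SNOT-22 subdomain scores, Lund-Kennedy endoscopic scores, and adverse effects" "were compared between prednisone and placebo groups at each time point using t-tests". Neither document mentions a repeated-measures model, an arm-by-visit term, baseline adjustment, an analysis set or a way of handling missing scores.

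The protocol confirms that these are repeated measurements on the same people. Section 2a says that at each visit "SNOT-22 and LundKennedy endoscopic exam scores will be repeated and recorded". Section 2g sets a single main comparison: "We will use the final scheduled appointment at 4 weeks after surgery as the official end point for comparison of treatment arms". It adds that "outcomes evaluated will be the symptom questionnaire and the endoscopic exam score at each visit". The SAP does not carry the 4-week point forward as primary; its nearest time is 1 month.

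Three protocol sections bear on who will have later scores. Section 2a says that once experimental therapy has ended, follow-up depends on how severe symptoms are and how the patient responds. Sections 2g and 6e say the same of follow-up beyond 4 weeks. Section 6d ends participation early for a patient with an adverse outcome of surgery or of postoperative therapy.

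**The concern.** Each patient can supply four correlated postoperative scores and a baseline score, yet each test uses one score per patient. Two things follow.

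First, a patient without a score at a visit drops out of that visit's test, although the other scores carry information about the missing one. If absence is unrelated to outcome, the cost is precision. If absence depends on symptoms, which SNOT-22 itself records, those who attend later visits are a selected group and the arm difference among them can be biased.

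Second, experimental therapy ends by two weeks and scores run to six months, so readers will want to know whether any early difference lasts. Four separate tests invite a comparison of p-values across visits, which does not test change.

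**Working it through.** **Inputs.** From the documents: four postoperative visits plus baseline, two arms, 50 patients required by the power analysis, 75 planned. Not in the documents: effect size, SD, alpha, power, allocation ratio, dropout and within-patient correlation. The values used for these below are assumptions.

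**The plan's own figure.** The required 50 cannot be reproduced, because none of its inputs is given. Working backwards with 25 per arm, two-sided 0.05 and 80% power, the implied standardised difference is d = (1.960 + 0.842) × √(2/25) = 0.79. It is used below only as a working value.

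**Precision at one incomplete visit.** Let m be the share missing at that visit and r the correlation with one other postoperative score that everyone has. Relative to complete data, the variance of the arm difference is:

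- t-test on those with a score: 1/(1 − m)
- model that also uses the other score: r² + (1 − r²)/(1 − m)

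The ratio of model to t-test is r²(1 − m) + (1 − r²) = 1 − m·r², so the saving is m·r².

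| m | r = 0.5 | r = 0.7 | r = 0.8 |
|---|---|---|---|
| 0 | 0% | 0% | 0% |
| 0.1 | 2.5% | 4.9% | 6.4% |
| 1/3 | 8.3% | 16.3% | 21.3% |

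**Adding baseline.** A longitudinal model was evaluated at month 6 with 25 per arm, equal correlation between all times, and dropout completely at random. With no missing data, the other postoperative scores give a variance ratio of 1.00 against the t-test. Adding baseline gives 0.91, 0.75 and 0.51 for r = 0.3, 0.5 and 0.7. With 20% to 30% missing at month 6 and r from 0.3 to 0.7, the other postoperative scores alone cut the variance by 3% to 18%, and with baseline by 11% to 53%. A model that omits baseline would forgo most of the available gain.

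**Bias if attendance follows symptoms.** Assume a constant effect of 0.50 SD, correlation 0.7 between the 1-month and 6-month scores, and odds of attending month 6 multiplied by e (weaker dependence) or e² (stronger) for each SD worse at 1 month. Take 29% to 45% missing, depending on arm. The expected difference among those who attend is about 0.45 SD in the weaker case and 0.39 SD in the stronger. Adjusting for the 1-month score recovers 0.50. Here the t-tests would suggest a fading effect when there was none.

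**Comparing p-values across visits.** Take d = 0.79 at every visit, 25 per arm and complete data, so each test has 80% power. The chance of significance at week 1 but not at month 6 is 80% minus the chance that both are significant: 13%, 11% and 9% for r = 0.3, 0.5 and 0.7. The direct test is the contrast of month 6 minus week 1, with standard error √[(2/25) × 2(1 − r)] = 0.335, 0.283 and 0.219. Its power to detect that a difference of 0.79 has vanished is 66%, 80% and 95%.

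**The case against.** The strongest reply is that the protocol asks for one comparison at 4 weeks, that a t-test at one visit is a legitimate randomised comparison, and that no stated objective concerns change over time. Much of this stands. Each t-test is valid at its visit if missingness is unrelated to outcome. It does not dispose of the point, because section 2g also makes the scores at each visit outcomes, and the SAP tests all of them without naming a primary time.

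A reader might infer three stronger things that the documents do not support:

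- **That one third of patients were expected to be lost**, from "The planned sample size was 75 patients" beside "By power analysis, we required 50 patients to achieve statistical significance". Sections 2g and 6e present 50 as the power-analysis number and as the point for considering early stopping. No dropout rate appears anywhere. Patients lost before any postoperative visit would also have no postoperative scores to borrow from, so the formula above would not apply to them.
- **That the plan cannot show whether an effect lasts.** The month-6 t-test does show whether a difference exists then. What is missing is a test of whether it has changed. Nor does the SAP say that it will infer fading from p-values; that is a risk in interpretation.
- **That the t-tests discard precision in every case.** With complete attendance the patient sets are identical across visits, and the other postoperative scores add nothing.

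That tests use only those with a score is itself an inference, but a t-test with no imputation rule leaves no alternative. Section 2a also sets a fixed schedule to 6 months, so symptom-dependent attendance is a possibility that the text raises, not an established fact.

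**Conclusion.** The point holds as a recommended improvement and does not invalidate the single-visit comparisons. The plan has no test of change in the arm difference. It also has no protection against selective absence at later visits, although the protocol's follow-up and early-termination wording makes such absence plausible.

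The precision at stake from one other postoperative score is small if few visits are missed (2% to 6% of the variance at 10% missing), moderate if many are (8% to 21% at one third missing), and nil if none are. These ranges rest on assumed missing shares and on correlations of 0.5 to 0.8. The size of any bias depends on how attendance relates to symptoms and cannot be estimated from the documents; the fall from 0.50 to 0.45 or 0.39 SD is an illustration.

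**What to change.** For SNOT-22 total, each SNOT-22 subdomain and Lund-Kennedy, fit one mixed model for repeated measures with arm, visit, arm-by-visit, baseline score and baseline-by-visit, and unstructured covariance across the four postoperative visits. Report the arm difference and 95% CI at each visit, including the one that represents the protocol's 4-week comparison point. Base any statement that an effect fades or persists on the arm-by-visit contrast with its CI, not on differing p-values. Report the number of scores at each visit by arm.

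Specify REML with Kenward-Roger or Satterthwaite degrees of freedom, both available for `mixed` in the Stata 15 already named. The default of maximum likelihood with normal-based intervals would be too narrow: at 25 per arm with complete data, the squared interval width is (48/50) × (1.96/2.011)² = 0.91 of the t-test's. That false narrowing of about 9% exceeds the true gain of 2% to 6% at 10% missing.

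The SAP is written in the past tense. If the t-tests have already been run, keep them and present the model beside them as a labelled reanalysis.

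The cost is a paragraph of SAP text and a few lines of code, with no new data. The model assumes that missingness is explained by the recorded scores. This is weaker than what the t-tests need, but it may fail for patients withdrawn for an adverse outcome that their scores do not reflect, so withdrawals should be reported by arm and reason.
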